5.2. Demographic and Baseline Characteristics

All demographic and baseline characteristic data will be summarized by planned overall treatment duration and overall using descriptive statistics for all subjects for each of the following analysis sets: SAF-Ext, FAS-Ext, FAS-Ext-I, PPS-Ext and PPS-Ext-I.

The summary table will include Ethnicity and Race, Region (US and non-US), Prior Anticholinergic Use (Yes/No), Prior Beta-3 agonist Use (Yes/No), Diabetes Mellitus (Yes/No), Baseline Hypertension (Yes/No), Pre-existing Hypertension (Yes/No), Age category 1 (<55, ≥55 to <65, ≥65 to <75, ≥75 years), Age category 2 (<65, ≥65 years), Age category 3 (<65, ≥65 to <85 years, ≥85 years), baseline average micturition episodes per day (≤ 12 vs > 12), Alpha blocker use with or without 5-ARI (with vs without), Urinary Incontinence (yes or no), total IPSS score, alpha blocker (tamsulosin, doxazosin, alfuzosin, other), and 5-ARI (finasteride, dutasteride, other).

Prior Anticholinergic Use and Prior Beta-3 agonist Use will be calculated from all prior medications documented on the Prior and Concomitant Medications electronic case report form (eCRF).

Baseline Hypertension will be defined as baseline systolic blood pressure (SBP) ≥ 140 mmHg or baseline diastolic blood pressure (DBP) ≥ 90 mmHg, regardless of medical history.

Pre-existing hypertension will be defined as having a medical history of hypertension or Baseline hypertension (baseline SBP ≥ 140 mmHg or baseline DBP ≥ 90 mmHg). The following list of preferred terms will be used to search for medical history of hypertension:

- Accelerated hypertension
- Diastolic hypertension
- Essential hypertension
- Hypertension
- Hypertensive crisis
- Hypertensive emergency
- Hypertensive heart disease
- Malignant hypertension
- Malignant hypertensive heart disease
- Secondary hypertension
- Supine hypertension
- Systolic hypertension

Age (years), height (cm), weight (kg), BMI captured at Screening on study URO-901-3005, and baseline IPSS total score will be summarized as a continuous variable.

Unless otherwise stated, percentages will be calculated out of the number of patients in the given analysis set.

All demographic data will be listed.

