7.3. Adverse Events

AEs will be coded using MedDRA version 23.0 or higher.

All reported AEs (whether treatment emergent or not) on both study URO-901-3005 and URO-901-3006 will be included in by-subject AE listings on the Safety Set Extension. Sorting will be by country, site, subject, date of event, SOC, PT and then verbatim description. An additional overall AE listing will be presented for subjects that were enrolled but not dosed with vibegron on URO-901-3006.

An AE will be considered treatment emergent (TEAE) if it begins or worsens in severity after the first dose of vibegron on study URO-901-3005 or URO-901-3006 through 5 days after the last dose of vibegron. Partial AE start dates will be imputed as detailed in [Section 4.2.3](#).

Summary tables will be based on TEAEs. The incidence of TEAEs will be presented using counts and percentages of subjects with TEAEs and tabulated by SOC and PT. SOC will be sorted in descending frequency and PT within SOC will be sorted by descending frequency based on the incidence across subjects overall. If a subject has multiple occurrences (start and stop) of an event associated with a specific SOC or PT within a SOC, a subject will only be counted once in the incidence count for the SOC or PT within SOC respectively.

An overall summary table of AEs will be presented detailing the number and percentage of subjects, and number of events for the following categories:

- At least one TEAE;

- At least one Treatment-Related TEAE;
- At least one Grade ≥ 3 TEAE (Mild = Grade 1, Moderate = Grade 2, Severe of Medically Significant = Grade 3, Life-Threatening = Grade 4, Death = Grade 5)
- At least one Grade ≥ 3 Treatment-Related TEAE;
- At least one Serious TEAE;
- At least one Serious Treatment-Related TEAE;
- At least one TEAE leading to Discontinuation from Study Medication;
- At least one TEAE of Special Interest;
- At least one Treatment-Related TEAE of Special Interest

Where not otherwise noted, all the following summaries are presented by PT:

- All TEAEs (by SOC and PT);
- Treatment-Related TEAEs (i.e., possibly or probably related);
- TEAEs occurring in 2% or more of the population;
- All TEAEs by SOC, PT, and maximum severity (where the maximum intensity per patient will be counted at each level of summarization);
- TEAEs with Grade ≥ 3 ;
- Treatment-Related TEAEs with Grade ≥ 3 ;
- Serious TEAEs;
- Treatment-Related Serious TEAEs;
- Fatal TEAEs;
- TEAEs leading to Discontinuation from Study Treatment;

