- TEAE of Special Interest (by protocol-defined AESI category);
- Treatment-Related TEAE of Special Interest (by protocol-defined AESI category);
- Non-fatal TEAEs;
- Hypertension TEAEs by Pre-existing Hypertension (Yes vs No) and Baseline Hypertension (Yes vs. No). Hypertension TEAEs will be selected as any TEAE with a preferred term of Hypertension.

In addition, a summary of all TEAEs by PT occurring in at least 2% of subjects will be created and ordered by descending overall frequency.

Adverse events of special interest for this study include:

- Adverse events consistent with urinary retention
- Adverse events suggestive of cystitis or urinary tract infection (UTI)
- Potential major cardiac and cerebrovascular events, including death (or any event with fatal outcome), myocardial infarction, cerebrovascular accident, hospitalization for unstable angina or chest pain, hospitalization for heart failure requiring hospitalization, and coronary revascularization/angioplasty/stent
- Adverse events consistent with hypertension (see protocol section 8.4.6)
- Adverse events consistent with orthostatic hypotension as confirmed by orthostatic vital signs
- Elevated serum aspartate aminotransferase (AST) or alanine aminotransferase (ALT) lab value requiring that study drug be temporarily withheld or permanently discontinued
- Neoplasms

Treatment listings will include the planned treatment duration, start and stop dates/times of the AE, study day (relative to start of double-blind treatment on URO-901-3005) and treatment day (relative to the day of first dose of vibegron). A treatment related AE is defined as an AE for which the investigator classifies the AE as being “Probably Related” or “Possibly Related” to study treatment on the Adverse Event CRF. Missing relationship and severity (intensity) will be imputed per Section 4.2.3.

The following additional listings will be provided:

- Listing of Deaths
- Listing of Serious TEAEs
- Listing of Treatment-Emergent AESIs
- Listing of TEAEs Leading to Withdrawal or Interruption of Study Treatment
- Listing of all AEs with a flag for TEAEs and onset (Prior = prior to first dose of vibegron or Treatment = on or after first dose of vibegron.)
- Listing of all medical history including pre-treatment adverse events with coded preferred terms in the hypertension AE search list:
 - Accelerated hypertension
 - Diastolic hypertension
 - Essential hypertension
 - Hypertension

- Hypertensive crisis
- Hypertensive emergency

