14.2.12.4	Overall Urgency-Related Leakage over Bladder Symptoms Based on [REDACTED]	FAS-Ext-I	Repeat 14.2.12.1
14.2.12.5	Overall Change of Bladder Symptoms Based on [REDACTED]	FAS-Ext-I	Categorical summary
14.2.12.1	[REDACTED] Domain Scores and Overall Satisfaction Score	FAS-Ext	Include CFB
Safety Endpoints			
14.3.1.1.1	Treatment Exposure	SAF-Ext	
14.3.1.1.1	Treatment Exposure	FAS-Ext	
14.3.1.2	Treatment Compliance	SAF-Ext	
14.3.1.3	Treatment Compliance	FAS-Ext	
Adverse Events			
14.3.2.1	Overall Summary of Treatment Emergent Adverse Events	SAF-Ext	
14.3.2.2	Treatment Emergent Adverse Events by System Organ Class and Preferred Term	SAF-Ext	Descending frequency of SOC and PT
14.3.2.3	Treatment-Related Treatment Emergent Adverse Events by Preferred Term	SAF-Ext	Descending frequency of preferred term

Title		Population	Programming notes
14.3.2.4	Treatment-Emergent Adverse Events by Preferred Term and Maximum Intensity	SAF-Ext	Descending frequency of preferred term
14.3.2.5	Treatment Emergent Adverse Events with Grade \geq 3 by Preferred Term	SAF-Ext	Descending frequency of preferred term
14.3.2.6	Treatment-Related Emergent Adverse Events with Grade \geq 3 by Preferred Term	SAF-Ext	Descending frequency of preferred term
14.3.2.7	Treatment-Emergent Adverse Events occurring in \geq 2% subjects by Preferred Term	SAF-Ext	Descending frequency of preferred term
14.3.2.8	Serious Treatment Emergent Adverse Events by Preferred Term	SAF-Ext	Descending frequency of preferred term
14.3.2.9	Treatment-Related Serious Treatment Emergent Adverse Events by Preferred Term	SAF-Ext	Descending frequency of preferred term
14.3.2.10	Treatment Emergent Adverse Events Leading to Discontinuation from Study Treatment by Preferred Term	SAF-Ext	Descending frequency of preferred term
14.3.2.11	Fatal TEAEs by Preferred Term	SAF-Ext	Descending frequency of preferred term
14.3.2.12	Treatment Emergent Adverse Events of Special Interest by Preferred Term	SAF-Ext	Descending frequency of preferred term
14.3.2.13	Treatment-Related Treatment Emergent Adverse Events of Special Interest by Preferred Term	SAF-Ext	Descending frequency of preferred term
14.3.2.14	Non-Fatal Treatment-Emergent Adverse Events by Preferred Term	SAF-Ext	Descending frequency of preferred term
14.3.2.15	Hypertension Treatment Emergent Adverse Events by Preferred Term, and Pre-Existing Hypertension	SAF-Ext	Descending frequency of preferred term

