14.3.2.16	Hypertension Treatment Emergent Adverse Events by Preferred Term, and Baseline Hypertension	SAF-Ext	Descending frequency of preferred term
14.3.2.17	Listing of Deaths	SAF-Ext	

Title		Population	Programming notes
14.3.2.18	Listing of Treatment Emergent Serious Adverse Events	SAF-Ext	
14.3.2.19	Listing of Treatment Emergent Adverse Events Leading to Withdrawal or Interruption of Study Treatment	SAF-Ext	
14.3.2.20	Listing of TEAEs of Special Interest	SAF-Ext	
Safety Labs			
14.3.3.1	Hematology Laboratory Parameters	SAF-Ext	Include observed and CFB
14.3.3.2	Clinical Chemistry Laboratory Parameters	SAF-Ext	Include observed and CFB
14.3.3.3	Urinalysis Laboratory Parameters	SAF-Ext	Include observed and CFB
14.3.3.4	Summary of Other Laboratory Parameters	SAF-Ext	
14.3.3.5	Abnormal Classification of Hematology Laboratory Parameters	SAF-Ext	
14.3.3.6	Abnormal Classification of Clinical Chemistry Laboratory Parameters	SAF-Ext	
14.3.3.7	Abnormal Classification of Urinalysis Laboratory Parameters	SAF-Ext	
14.3.3.8	Abnormal Classification Summary of Other Laboratory Parameters	SAF-Ext	
14.3.3.9	Shift Table of L/N/H Classification for Hematology Laboratory Parameters	SAF-Ext	
14.3.3.10	Shift Table of L/N/H Classification for Chemistry Laboratory Parameters	SAF-Ext	
14.3.3.11	Maximum Post-baseline ALT and AST vs. Maximum Post-baseline Bilirubin	SAF-Ext	

Title		Population	Programming notes
14.3.3.12	Listing of Subjects who Potentially Met Hy’s Law	SAF-Ext	
14.3.3.13	Summary of Liver Function Laboratory Findings	SAF-Ext	
Vital Signs			
14.3.4.1	Vital Sign Parameters	SAF-Ext	Include all observed and CFB
14.3.4.2	Vital Sign Parameter Change from Baseline Shifts at 3 Consecutive Visits	SAF-Ext	SBP, DBP and PR
14.3.4.3	Vital Sign Parameter Change from Baseline Shifts at Week 52	SAF-Ext	SBP, DBP and PR
14.3.4.4	Vital Sign Parameter Maximum Post-Baseline Change from Baseline	SAF-Ext	SBP, DBP and PR
Other			
14.3.5.1	Post-Void Residual Volume	SAF-Ext	
14.3.6.1	Total IPSS score	SAF-Ext	
14.3.7.1	Physical Examination Shift from Baseline	SAF-Ext	

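### Tables 14.3.2.15 and 14.3.2.16 select hypertension TEAEs by one preferred term, although the SAP has its own 12-term hypertension list, so these two tables could undercount

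*SAP*

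**What the plan says.** SAP 7.3 includes among its planned summaries "Hypertension TEAEs by Pre-existing Hypertension (Yes vs No) and Baseline Hypertension (Yes vs. No"), and then fixes the selection: "Hypertension TEAEs will be selected as any TEAE with a preferred term of Hypertension". SAP 11.1.1 gives the two resulting tables. Table 14.3.2.15 is titled "Hypertension Treatment Emergent Adverse Events by Preferred Term, and Pre-Existing Hypertension" and Table 14.3.2.16 "Hypertension Treatment Emergent Adverse Events by Preferred Term, and Baseline Hypertension".

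The SAP also carries a longer list of hypertension terms, printed twice:

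- SAP 5.2, in defining pre-existing hypertension: "The following list of preferred terms will be used to search for medical history of hypertension".
- SAP 7.3, among the additional listings: "Listing of all medical history including pre-treatment adverse events with coded preferred terms in the hypertension AE search list".

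Pre-existing hypertension (SAP 5.2) is a history of hypertension found with that list, or a raised blood pressure at baseline. Baseline hypertension is defined by blood pressure alone.

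**The concern.** Long-term safety is the primary objective, and hypertension is a predefined adverse event of special interest. The two tables are where a reader would look to see whether hypertension events on vibegron differ between men with and without prior hypertension. History is searched with 12 terms and the on-treatment outcome with one. An event coded to another term, including the terms that denote acute severe forms, would be absent from both tables.

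The same code can also be treated differently before and after the first vibegron dose. SAP 5.4 counts as medical history any adverse event that ended before active treatment. A subject on placebo in the parent study whose event coded to essential hypertension and resolved in that time can therefore be classed as having pre-existing hypertension. The same code arising on vibegron would not enter Table 14.3.2.15 as a hypertension event.

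**Working it through.** No sample size, power or event-rate figure is involved, so the check is a comparison of the SAP's own definitions.

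**1. The list.** The terms in SAP 7.3 are: accelerated, diastolic and essential hypertension; hypertension; hypertensive crisis; hypertensive emergency; hypertensive heart disease; malignant hypertension; malignant hypertensive heart disease; and secondary, supine and systolic hypertension. That is 12 terms. SAP 5.2 has the same 12.

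**2. Where each definition applies.**

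| Use | SAP section | Preferred terms |
|---|---|---|
| Medical-history part of pre-existing hypertension | 5.2 | 12 |
| Listing of history and pre-treatment adverse events | 7.3 | 12 |
| Hypertension TEAEs, Tables 14.3.2.15 and 14.3.2.16 | 7.3, 11.1.1 | 1 |

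Terms left out of the two tables: 12 − 1 = 11.

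The mismatch between grouping variable and outcome arises in Table 14.3.2.15. In Table 14.3.2.16 the grouping variable rests on blood pressure, so there the issue is only the narrow outcome.

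**3. Direction.** Let A be the number of subjects with at least one TEAE coded *Hypertension*, and B the number with at least one TEAE coded to any of the 12 terms. Everyone in A is also in B, so A ≤ B. The shortfall B − A is the number of subjects whose hypertension-type TEAEs all code to the other 11 terms. A subject with both kinds of code is already counted in A. The one-term rule can therefore lower the count in these tables but never raise it.

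**4. Size.** The documents give no event counts or coding frequencies, so B − A cannot be computed. It is zero if every relevant subject has at least one event coded *Hypertension*.

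**5. Other planned displays.**

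- All TEAEs are tabulated: "All TEAEs (by SOC and PT"). An event under any of the 11 terms appears there under its own term, and also in the Grade 3 or higher, serious, fatal or discontinuation tables if it qualifies.
- The special-interest events include "Adverse events consistent with hypertension (see protocol section 8.4.6"), a category not tied to one preferred term. Tables 14.3.2.12 and 14.3.2.13 are not split by prior hypertension.
- SAP 7.5 splits blood pressure and pulse changes by pre-existing hypertension, but these are measurements, not adverse events.

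No other adverse event table in SAP 11.1.1 is split by prior hypertension status.

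**The case against.** The strongest reply is that nothing disappears from the report and no stated rule is broken. Four parts of it deserve a direct answer.

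- **Visibility elsewhere.** A reader might infer that a hypertensive crisis or emergency on treatment would go unreported. The documents do not support that. It would be in the all-TEAE tables and the adverse event listing, and in the severity, serious and special-interest displays where it qualifies. With the listing of hypertension history, such an event could be matched by hand to the subject's prior status. This part stands and confines the point to two tables.
- **The purpose of the list.** A reader might also infer that the SAP breaks its own rule for on-treatment events. It does not. Although SAP 7.3 calls it an adverse event search list, the text attaches it to medical history and pre-treatment events. Several terms, such as essential hypertension and hypertensive heart disease, describe standing diagnoses, and a sensitive list is reasonable for history. This stands too: the matter is an unexplained difference of definition. It does not explain why the acute terms are left out of the on-treatment outcome.
- **The table titles.** Presentation by preferred term might suggest that several terms were intended. SAP 7.3 makes that the default layout for its summaries, so the titles prove little.
- **The special-interest definition.** Protocol 8.4.6 defines the hypertension category by blood pressure criteria that depend on parent-study baseline, or by starting or increasing antihypertensive medication. That is a fuller capture of hypertension than any preferred term. It still gives no event count by prior hypertension status.

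It is also fair to say that the safety analysis has no inferential testing (SAP section 7), and that no decision rule depends on these tables.

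**Conclusion.** The point holds for Tables 14.3.2.15 and 14.3.2.16 only. They use 1 of the SAP's 12 hypertension terms, they are the only adverse event tables split by prior hypertension status, and the SAP gives no reason for the narrower rule. They could undercount subjects whose events code to any of the other 11 terms.

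The direction follows from the definitions and needs no assumption. The size does, and the documents offer no basis for one: it may be zero if events code almost always to *Hypertension*. A reader might be tempted to convert a guessed share of events into an understated incidence. That is unsupported, because the incidence tables count subjects, and a subject with a second event coded *Hypertension* is already included. The conclusion is that the two tables may be incomplete for their stated purpose, not that the trial's hypertension reporting as a whole is.

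**What to change.** In SAP 7.3, replace the one-term selection for Tables 14.3.2.15 and 14.3.2.16 with the 12-term list already printed there. Show a row for each preferred term, so that *Hypertension* alone stays visible, and add a row counting each subject once for any of the terms.

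The cost is one changed sentence, a matching programming note in SAP 11.1.1, and at most 11 further preferred-term rows plus the any-term row in each table. No new data or recoding is needed.

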7.4. Laboratory Evaluations

All continuous laboratory parameters will be summarized descriptively by absolute value at each visit together with the corresponding changes from baseline. All parameters will be summarized in SI units.

The number and percentage of subjects with laboratory measurements outside of the central laboratory normal range will also be summarized by visit. Shift tables from baseline to maximum post-baseline value, to minimum post-baseline value, last post-baseline value, and at each post-baseline visit will be provided for hematology and chemistry parameters to display low, normal, high, and missing values by treatment group in a 3-by-3 contingency table. Denominators for percentages will be the number of subjects with non-missing data at the specific assessment and baseline.

ALT/AST and Total Bilirubin will be displayed as eDISH plots. Maximum post-baseline total bilirubin will be presented (<2 and ≥ 2 x ULN) and plotted against maximum post-baseline ALT (<3 , ≥ 3 - <5 , ≥ 5 - <10 , and ≥ 10 x ULN), expressed as multiples of ULN. This will be repeated to show maximum post-baseline total bilirubin against maximum post-baseline AST.

Data for subjects with ALT or AST ≥ 3 x ULN, and bilirubin ≥ 2 x ULN will be presented, which will include all visits for this subset of subjects. A line plot of liver biochemistry test results (including ALP, ALT, AST, total bilirubin, and GGT) over time will also be presented for this subset of patients.

A sample for the urinalysis and urine culture will be sent to the central laboratory only if the urine dipstick performed at the site tests positive for the presence of leukocytes, nitrites, or blood cells. Central urinalysis data will be provided only in the listing.

Any data outside the central laboratory normal reference ranges will be explicitly noted on the listings that are produced.

7.5. Vital Sign Assessments

Vital sign data including blood pressure, pulse rate, respiration rate, body temperature and weight will be collected at all study visits except for the Week 1, Week 16, and 44 telephone visits. Height will be measured at Screening only. Blood pressure will be measured in triplicate at each visit. The average of triplicates will be used for summary. For subjects in URO-901-3005 Study Part 1 at any visits with orthostatic blood pressure measurements: blood pressure (in triplicate) and pulse rate taken pre-dose in sitting position are equivalent to all other pre-dose vital sign values and will be used. Orthostatic and standing blood pressure measurements collected during Part 1 of URO-901-3005 will not be included in any summaries on URO-901-3006.

For all parameters, absolute values and change from baseline will be presented for scheduled visits using descriptive statistics for continuous variables. In addition, the maximum post-baseline change from baseline value and change from baseline to the end of treatment will be summarized for each of the vital signs.

To further investigate changes in SBP/DBP/pulse rate from baseline, the following tables will be prepared:

- Counts and percent of subjects in each group with at least a 5/10/15 CFB at 2 consecutive post-baseline visits and at Week 52 will be produced for all subjects, by pre-existing hypertension category (Yes/No) and by pre-existing hypertension category (Yes/No).
- Maximum post-baseline CFB (including 95% CI of Mean)

The line plot of mean (SE) of change from baseline in blood pressure and pulse rate over time will be prepared. A by-subject listing, sorted by subject identifier, will be presented including all vital sign results (scheduled or unscheduled).

